### Study design

For this analysis we will use the database of the two randomized clinical trials, named the 'High versus Low Positive End–expiratory Pressure During General Anesthesia for Open Abdominal Surgery (PROVHILO) [3], and the 'PRotective Ventilation with Higher versus Lower PEEP during General Anesthesia for Surgery in OBESE Patients' (PROBESE) [9]. PROVHILO and PROBESE investigated the effects of an open lung approach during low tidal volume ventilation in patients undergoing major surgery.

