# Statistical analysis plan

Demographic, clinical and outcome variables are presented as medians with interquartile ranges (IQR), or number with percentage, where appropriate. Differences in baseline characteristics between patients with and patients without hypocapnia will be analyzed using the Pearson Chi–squared or Fisher exact tests for categorical variables and with a one–way ANOVA or Kruskal–Wallis test for continuous variables.

Data points for intraoperative variables (vital signs, ventilator settings and ventilation parameters) will include those collected in the first, second and third hour after start of the study, and before extubation.

Occurrence of postoperative pulmonary complications will be compared using a Fisher's exact test, time to event analyses will be performed using a Cox proportional hazard model or a competing risk model where appropriate. Next, we will perform a propensity matched cohort. Patients will be matched 1:1 with a maximum caliper of 0.02. The following covariates will be used for propensity matching: age, gender, BMI, type of surgery, compliance, history of COPD. We will calculate interaction term for the ARISCAT score as sensitivity analysis. We will perform time-weighted analysis for etCO2 levels in the primary end-points. Kaplan-Meier curve will be used to plot the relation between hypocapnia and the primary outcome.

A LOESS regression will be used to visualize the relationship of etCO2 as a continuous variable with the primary outcome. The association between etCO2 and the primary outcome will be determined using a generalized mixed model in which age, gender, BMI, type of surgery, compliance and history of COPD will be used as covariates. Sankey plot will be used to demonstrate flow association between etCO2 and primary or secondary outcomes.

As a sensitivity analysis the main analyses will be repeated in obese patients and non-obese patients, using a cutoff of 30 kg/m^2 for BMI. Another sensitivity analysis will be performed to determine the effect of PEEP settings on outcome. For this analysis the interaction term for PEEP on the generalized mixed model will be calculated.

A P–value of < 0.05 will be considered statistically significant. All analyses will be performed with R statistics version 4.0.4.

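### The analyses above and below BMI 30 have no planned formal comparison, and a difference between them could reflect the parent trial rather than obesity

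*Combined protocol and SAP*

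**What the plan says.** The Statistical analysis plan section states: "As a sensitivity analysis the main analyses will be repeated in obese patients and non-obese patients". The cutoff is 30 kg/m², and a single P < 0.05 threshold covers all analyses. No interaction term, heterogeneity test or other contrast between the two BMI subsets is given.

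The same section does plan interactions for two other variables. For ARISCAT: "We will calculate interaction term for the ARISCAT score as sensitivity analysis". For PEEP: "For this analysis the interaction term for PEEP on the generalized mixed model will be calculated".

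BMI otherwise enters only as an adjustment variable. For the matching: "The following covariates will be used for propensity matching: age, gender, BMI, type of surgery, compliance, history of COPD". For the regression: "The association between etCO2 and the primary outcome will be determined using a generalized mixed model", with the same six covariates (the list ends "compliance and history of COPD will be used as covariates"). Parent trial is in neither list, and the random effects of the mixed model are not stated.

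Under Study design, the titles describe PROBESE as a trial "during General Anesthesia for Surgery in OBESE Patients" and PROVHILO as one "During General Anesthesia for Open Abdominal Surgery (PROVHILO". Study details refers the full eligibility criteria to the original publications. Among the Planned inserts, the item by parent trial is eTable 1, a table of patient characteristics. eTable 3 holds the sensitivity analyses.

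**The concern.** There are two separate problems.

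First, results from two subsets, each judged at P < 0.05, invite the reading that an association is present in one group and absent in the other. That pattern arises easily when the association is identical in both. The subsets are disjoint, so a reader could compare the estimates by hand, but the plan does not say that this will be done.

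Second, obesity and parent trial are entangled. If PROBESE enrolled only patients with BMI 30 or more, every non-obese patient comes from PROVHILO, and the obese subset is PROBESE plus any obese PROVHILO patients. An etCO2 association that differs between the trials for any reason other than BMI would then look like a difference by obesity. A random intercept for trial, if intended, would absorb a difference in baseline risk but not a difference in the etCO2 association.

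**Working it through.** The plan gives no sample size, event rate, BMI distribution or effect size, so there is no figure of its own to reproduce. **Every numerical input below is an assumption.** Tests are taken as two-sided at 5%, because the plan does not state sidedness.

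**1. Same association in everyone: how often do the subsets disagree?** If the subset powers are a and b, the chance that exactly one subset is significant is a(1 − b) + b(1 − a). With no association this is 2 × 0.05 × 0.95 = 0.095.

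Worked case with binary hypocapnia, unadjusted: 2000 obese and 700 non-obese patients, 65% hypocapnic, risk 20% and 35% in those without hypocapnia, common odds ratio (OR) 1.3, ln 1.3 = 0.262.

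- Obese: 1300 with and 700 without hypocapnia. Odds 0.25 × 1.3 = 0.325 give a risk of 0.245. Variance = 1/319 + 1/981 + 1/140 + 1/560 = 0.0131, SE 0.114, z = 2.29, power a = 0.63.
- Non-obese: 455 with and 245 without. Odds 0.538 × 1.3 = 0.70 give a risk of 0.412. Variance = 1/187.4 + 1/267.6 + 1/85.75 + 1/159.25 = 0.0270, SE 0.164, z = 1.60, power b = 0.36.
- Exactly one significant: 0.63 × 0.64 + 0.36 × 0.37 = 0.54.

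With subsets of 2000/700 or 1500/800 the range is 50–54% at OR 1.3 and 3–5% at OR 1.8.

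Continuous etCO2, as in the mixed model, was examined in 72 scenarios using logistic models fitted to expected outcomes:

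- PROBESE/PROVHILO sizes 1900/850 or 1500/1000.
- PROBESE BMI of 30 plus a gamma variable, mean/SD 36/4, 39/6 or 42/6. PROVHILO BMI normal, 25.5/4, 26/4.5 or 26.5/5. This makes 13–25% of PROVHILO obese (110–244 patients).
- Complication risks 20/35, 15/25, 20/20 or 30/30%.
- etCO2 standardised with the same distribution in both trials, no site clustering and no other covariates.

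| Common OR per SD lower etCO2 | Exactly one subset P < 0.05 |
|---|---|
| 1.0 | about 10% |
| 1.1 | 38–51% |
| 1.15 | 50–59% |
| 1.2 | 35–54% |
| 1.3 | 6–25% |
| 1.4 | 1–8% |

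**2. Trials differ, BMI has no effect.** Take OR 1.3 in PROBESE and 1.0 in PROVHILO. The non-obese subset, all from PROVHILO, shows 1.0. The obese subset shows roughly exp(q × ln 1.3), where q is PROBESE's share of it. By head count q runs from 1500/1744 = 0.86 to 1900/2010 = 0.95, giving 1.25 to 1.28. The fitted models, which weight by information rather than head count, give 1.23–1.28.

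| True ORs (PROBESE vs PROVHILO) | Ratio of subset ORs | etCO2-by-BMI ratio per 10 kg/m², trial main effect only | Rejection rate | With etCO2-by-trial added |
|---|---|---|---|---|
| 1.3 vs 1.0 | 1.23–1.28 | 1.11–1.17 | 44–69% | ratio 1.00, 5% |
| 1.2 vs 1.0 | 1.16–1.19 | 1.08–1.12 | 24–40% | ratio 1.00, 5% |

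A BMI interaction alone would therefore not cure the problem. The etCO2-by-trial term is needed as well.

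**3. Precision of the corrected analysis.** Let the OR be 1.1 per SD at BMI 30, multiplied by 1.10 per 5 kg/m², that is 1.10² = 1.21 per 10 kg/m².

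| Model | Power | 95% CI factor on the ratio |
|---|---|---|
| Pooled, with etCO2-by-trial | 32–70% | 1.16–1.29 |
| PROVHILO only | 14–29% | 1.30–1.53 |
| Pooled, trial main effect only | 67–99% | biased if the trials differ |

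For binary hypocapnia within PROVHILO, take 200 obese (OR 1.5) and 800 non-obese (OR 1.0), 65% hypocapnic and unexposed risk 35%. SE = √(0.0939 + 0.0242) = 0.344, z = 0.405/0.344 = 1.18, power 22%, CI factor exp(1.96 × 0.344) = 2.0. With 100 and 700 patients, power is 14% and the factor 2.5.

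**The case against.** The plan calls the split a sensitivity analysis. Neither the Hypothesis nor the Objectives section asks whether obesity modifies the association. Repeating an analysis in each population to see whether the result is robust is legitimate, and the choice of subset repeats for BMI but interactions for ARISCAT and PEEP may be deliberate. Type of surgery is in both covariate lists, a trial-level random effect may be intended, and eTable 1 describes patients by study. PROBESE's BMI criterion is not in the documents. All magnitudes are assumed, disagreement is only 1–8% at OR 1.4, and the corrected analysis has little power.

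Most of this stands, and it keeps the point minor. It does not remove it. Adjusting for type of surgery, or adding a trial intercept, changes baseline risk but does not separate an etCO2 association that differs by trial from one that differs by BMI. The absence of a planned comparison does not depend on PROBESE's entry criterion. Low power favours an estimate with an interval over two P-values placed side by side.

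**Conclusion.** The concern holds as a minor point. From the text alone, no formal comparison by BMI is planned and parent trial is in neither covariate list. That the split is largely a split by trial is likely from the titles but not confirmed, because it depends on PROBESE's BMI criterion and on the number of obese patients in PROVHILO.

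The size is illustrative. Spurious disagreement between subsets is common at modest associations (roughly 35–59% for ORs of 1.1–1.2 per SD) and uncommon at stronger ones. A difference that exists only between trials passes almost in full into the apparent obesity contrast. The consequence is limited to how an exploratory analysis is interpreted.

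**What to change.** - In the generalized mixed model, pre-specify an etCO2-by-BMI interaction (BMI continuous) together with parent trial and an etCO2-by-trial term. If binary hypocapnia is preferred as the exposure, name that as a separate model.
- Base any statement about obesity on the interaction estimate with its 95% confidence interval, labelled exploratory. Support it with the same contrast within PROVHILO, where trial is fixed.
- In eTable 3, show the BMI-30 subset estimates descriptively, with confidence intervals and the number of patients from each trial in each subset.
- Check PROBESE's BMI criterion. If it confirms this, state that the non-obese subset comes only from PROVHILO.
- State that a non-significant interaction is not evidence of no difference.

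The cost is one model, one supporting contrast and a few sentences in the SAP, all on data already in hand. The limits should be stated: low precision, an assumed linear BMI effect in the pooled interaction, and BMI and trial that may be only partly separable.

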# **Planned inserts**

- Figure 1: CONSORT
- Figure 2: Sankey plots
- Figure 3: distribution plots of ventilation characteristics
- Figure 4: LOESS regressions
- Figure 5: Kaplan-Meier curve
- Table 1: Patient characteristics

Table 2: Intraoperative characteristics, including ventilation and hemodynamic characteristics

Table 3: Comparison of outcomes between the patients with or without hypocapnia

- eTable 1: Patient characteristics for studies
- eTable 2: Ventilation characteristics
- eTable 3: Sensitivity analyses
